## 11.8 EXIT OF SUBJECTS

An Exit Case Report Form will be completed for all subjects, either when they complete the study or if they exit early.

It is the responsibility of the investigator to provide complete follow-up data to AMO for each subject, and every attempt will be made to gather that complete follow-up data for all subjects enrolled as missing data can have a negative effect on the study results..

Patients who would be traveling, relocating or otherwise unavailable for postoperative follow-up visits should not be chosen for this clinical study.

#### SUBJECT FOLLOW-UP

To minimize subjects lost to follow-up, subjects will be provided compensation for their time and participation in the study at the 1- and 6-month postoperative exams.

Additionally, sites will be compensated for completion of the 1- and 6-month exams and will be provided frequent listings of upcoming 1- and 6-month subject examinations as well as follow-up reminder cards to send to the subjects. It is anticipated that at least 90% of subjects will be available for the 6-month study visit (i.e., no more than a 10% lost-to-follow-up rate at 6 months postoperatively). If a subject has a confirmed report of severe visual distortion(s) per the questionnaire, prior to the 6-month exam, every effort is to be made to ensure that subject returns for the 6-month exam. The investigative site shall make a minimum of at least three attempts (phone calls/emails and/or letters) to locate missing subjects.

#### SUBJECT DISCONTINUATION

Subjects will be discontinued from the study if the study lens is removed or if the subject dies. Subjects will be considered "lost-to-follow-up" from the study only if irretrievably lost for unavoidable reasons such as: subject moved/unable to locate, subject uncooperative/refuses further study participation, subject ill/unable to travel. The site shall document at least three attempts (phone calls/emails and/or letters) to locate lost-to-follow-up subjects and the investigator should notify AMO prior to exiting a subject from the study. If a subject is exited from the study, the investigator will, if at all possible, have the subject return for a final study visit. In the event of subject relocation, efforts must be made by the investigator to secure follow-up information (i.e., slit-lamp findings and general visual acuity, etc.) from the subject's new physician.

If a subject is exited early from the study, the investigator will complete an Exit Case Report Form indicating the reason for study exit. In the event of a lens removal or other serious adverse event, the subject may be exited from the study; however, efforts must be made by the investigator to follow the subject until resolution of the adverse event.

Note: A subject may be exited from the study if complications occur during the first-eye surgery and the planned study lens is not implanted; however, the eye will be followed until the resolution of the complication prior to exiting the subject from the study. If a complication occurs during the second-eye surgery and the planned study lens is not implanted in the second eye, the subject is to be followed according to the protocol for

the first eye (although data may be analyzed separately), and the second eye will be followed for safety until resolution of the complication.

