### **4. STUDY DESIGN**

This study is a prospective, multicenter, bilateral, non-randomized, open-label, clinical study conducted at up to 20 sites in the USA. Subjects will be bilaterally implanted with the high cylinder TECNIS Toric IOLs, Model ZCT300-ZCT600 with at least one eye of each subject implanted with TECNIS Toric IOL, Models ZCT450 or ZCT525 or ZCT600. The fellow eye will be implanted with a high cylinder TECNIS Toric IOL, Model ZCT300-ZCT600 as chosen by the surgeon.

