If a subject reported a severe visual distortion in the questionnaire or experienced a serious or device-related adverse event at any unscheduled study visit, uncorrected distance visual acuity, best corrected distance visual acuity, manifest refraction, keratometry, intraocular pressure and biomicroscopic slit-lamp examinations will also be performed.

A 1-year examination will be required only if the subject reports a severe visual distortion at the 6-month examination or experienced an IOL repositioning procedure (due to IOL misalignment during the study).

If a serious or device-related adverse event occurs at or prior to the 6-month visit, details of the event will be collected at the time of the event using an adverse event form. If the adverse event results in an IOL repositioning procedure due to misalignment, the questionnaire should be administered prior to the procedure to collect information regarding visual distortions. Keratometry and toric IOL axis measurements will be performed prior to the repositioning procedure to collect data regarding the IOL misalignment.

A chart summary of all examination procedures required at each study visit is provided in Appendix A.

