## **12.5 ADVERSE EVENT FOLLOW-UP**

For every serious or device-related adverse event, appropriate measures should be undertaken to treat and/or monitor the subject until resolution occurs. Obtain and maintain in the subject's files all pertinent medical data relating to the event including the subject's medical records and medical reports and/or judgments from colleagues or outside specialists who assisted in the treatment and follow-up of the subject. The investigator should keep AMO closely informed as to the outcome of serious and/or device-related adverse events, thereby allowing AMO to comply with the appropriate regulatory reporting requirements. A Serious and/or Device-Related Adverse Event Update CRF should be completed each time the subject returns to the investigator or other specialist(s) for follow-up of serious and/or device-related adverse event until resolution of the event. Any subject who is exited from the study due to a serious and/or device-related adverse event will be followed until the outcome is determined.

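### Section 11.8 gives two conflicting rules for lens removal and says nothing about the other eye, so scheduled data on an eye that still holds a study lens can be lost

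*Protocol*

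**What the plan says.** Protocol section 4 makes the study bilateral: "Subjects will be bilaterally implanted with the high cylinder TECNIS Toric IOLs". Each subject is therefore meant to carry two study lenses.

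Section 11.8, Subject Discontinuation, deals with lens removal twice:

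- The first paragraph is mandatory: "Subjects will be discontinued from the study if the study lens is removed or if the subject dies".
- The next paragraph is permissive: "In the event of a lens removal or other serious adverse event, the subject may be exited from the study".

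The same subsection adds safeguards. After a removal, "efforts must be made by the investigator to follow the subject until resolution of the adverse event". On any exit, "the investigator will, if at all possible, have the subject return for a final study visit". Section 12.5 goes further on the event: it requires follow-up to a known outcome whenever a serious or device-related event is the reason for exit.

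The closing Note of the subsection covers lenses that were never implanted. If the first-eye lens is not implanted because of a complication, the subject may be exited. If the second-eye lens is not implanted, "the subject is to be followed according to the protocol for" whichever eye was implanted first, and the second eye is followed for safety until the complication resolves. No comparable statement covers a lens that was implanted and later removed.

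**The concern.** The two sentences cannot both be applied. With up to 20 sites, one investigator can end participation at removal and another can keep the subject in the study, and each would be following the text.

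Both sentences are also written as if a subject had one lens. Under the mandatory sentence, removal from one eye ends the scheduled visits for both. The retained eye, which may itself hold a ZCT450, ZCT525 or ZCT600, would then have no scheduled 6-month examination.

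The retained eye can be either the primary or the fellow eye as the SAP defines them. SAP section 4.4 and Appendix I report refraction, monocular acuity and lens findings at 6 months, and adverse events at any postoperative time, for primary and for fellow eyes. SAP section 4.2 and Appendix I do the same for axis misalignment. An eye that leaves these tables because of what happened to its partner is not missing at random in any obvious sense. The loss would also vary with how each site read section 11.8.

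**Working it through.** The point rests on wording, so the first step sets the provisions side by side.

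| Situation | Rule for the subject | Rule for the other eye |
|---|---|---|
| Study lens removed (11.8, first paragraph) | Discontinued, mandatory | None stated |
| Study lens removed (11.8, next paragraph) | Exit optional, event followed to resolution | None stated |
| Second-eye lens never implanted (11.8, Note) | Stays in the study | First eye followed per protocol |
| Exit for a serious or device-related event (12.5) | Event followed until outcome is determined | None stated |

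The first two rows conflict. Only the third row has an eye-specific rule, and it does not extend to removal. Sections 11.8 and 12.5 secure the event, but neither puts the retained eye on the visit schedule.

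**Follow-up at stake.** The 6-month window is days 120 to 180 after the second implant (Protocol Table 4). If a lens is removed on day *d* and the subject exits then, the retained eye forgoes 120 − *d* to 180 − *d* days of scheduled follow-up. The documents give no value for *d*; as illustrations:

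- *d* = 30: 120 − 30 = 90 to 180 − 30 = 150 days.
- *d* = 60: 120 − 60 = 60 to 180 − 60 = 120 days.

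A removal after the 6-month visit costs none of the 6-month data.

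**Number of eyes.** No removal rate is given. Assuming 1 to 3 removals among the 80 bilateral subjects: 1/80 = 1.25% and 3/80 = 3.75%. Each costs one retained eye only if the removal is in one eye, falls before the 6-month visit, is followed by exit, and leaves a study lens in the other eye. For scale, section 11.8 anticipates up to 10% loss to follow-up, which is 0.10 × 80 = 8 subjects.

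**Primary endpoint.** The sample-size figure reproduces: with N = 80, a true rate of 0.025 and an exact (Clopper-Pearson) 95% interval, the half-width is at most 0.05 when 3 or fewer subjects are severe, and P(X ≤ 3) = 0.859, the stated 86%. Lens removal does not take subjects out of this calculation. Protocol 20.2 and SAP 2.1 carry forward pre-removal data, and count a removal with no earlier questionnaire as severe. As an illustration, take 0.025 × 80 = 2 severe reports plus 1 to 3 removals with no earlier questionnaire:

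| Removals | Planned rule: counted as severe (95% CI) | If dropped instead (95% CI) |
|---|---|---|
| 1 | 3/80 = 3.75% (0.8 to 10.6) | 2/79 = 2.5% (0.3 to 8.9) |
| 2 | 4/80 = 5.0% (1.4 to 12.3) | 2/78 = 2.6% (0.3 to 9.0) |
| 3 | 5/80 = 6.25% (2.1 to 14.0) | 2/77 = 2.6% (0.3 to 9.1) |

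The plan uses the first rule, so a removal stays in the primary rate even if the subject exits. The exposure is confined to the by-eye data.

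**The case against.** The strongest reply is that the plan already looks after these subjects. Sections 11.6, 11.8 and 12.5 require the event to be followed to resolution or outcome, a final visit is to be sought, and the primary endpoint keeps the removal. Under the permissive sentence the subject can simply stay. The affected tables are descriptive, carry no test or success criterion, and would lose very few eyes next to the loss the plan already tolerates. The Note is also not a clean precedent, because its first half allows exit.

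Most of this stands, and it limits the size of the point. It does not remove it. The safeguards attach to the event and to one exit visit made if possible. They do not provide a 6-month examination of the retained eye or capture an unrelated adverse event that arises there after exit. The permissive sentence helps only at sites that choose it over the mandatory one. The second half of the Note is the closer parallel, since there too one eye holds a study lens and the other does not.

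Two stronger readings are tempting, and the documents do not support them.

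- A reader might infer that follow-up of the removal itself stops early. It does not: the scheduled visits can end, but follow-up of the event is required.
- A reader might infer that leaving removal out of the 1-year triggers is an error. Section 11.1 says "A 1-year examination will be required only if the subject reports a severe visual distortion at the 6-month examination" and then adds repositioning for misalignment. That is consistent with Protocol Table 4 and Appendix A. It also has a rationale, since a repositioned lens can still be assessed for axis and a removed one cannot. Adding removal there would be a preference, not the repair of a contradiction.

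**Conclusion.** The point holds in a limited form. Section 11.8 contradicts itself on whether lens removal ends participation, and it has no rule for a retained study lens in the other eye. The consequence is possible loss of that eye's scheduled 6-month acuity, refraction, axis and lens-finding data, and of its later adverse events. That loss would be linked to the partner eye's outcome and could differ between sites.

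The size is probably small: on the assumed 1 to 3 removals, at most 1 to 3 retained eyes, in descriptive tables only. That range is an assumption, as is the timing of removal. The primary rate and the 86% precision statement are unaffected. The correction is still worth making, because the study's stated purpose includes continued safety of these lenses and the change is cheap.

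**What to change.** Reconcile the two sentences in section 11.8 with each other and with section 12.5, and say which eye is meant. Then state, for data collection only:

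- A subject with one study lens removed stays on the existing visit schedule through the 6-month visit, for safety and for the other eye if it still holds a study lens. This follows what the Note already provides when the second-eye lens is not implanted.
- The eye from which the lens was removed stops contributing lens-performance data such as refraction and axis. Its adverse event follow-up continues as sections 11.8 and 12.5 already require.

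This takes no position on when a lens should be removed or how the removal is managed. The carry-forward and counted-as-severe rules for the primary endpoint need no change, and neither do the 1-year triggers.

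The cost is a few sentences and, for perhaps 1 to 3 subjects on the assumption above, visits that are already on the schedule. Subjects remain free to withdraw.

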### **11.9 PROTOCOL DEVIATIONS**

Any departure from the protocol procedures represents a protocol deviation. Protocol deviations may be subject-based (e.g., inclusion/exclusion criteria, informed consent deviation, etc.) or procedural-based (e.g., out-of-interval visits, non-compliance with testing procedures, etc.). All protocol deviations will be documented using protocol deviation case report forms. Any deviation made to protect the life or physical well-being of a subject in an emergency as well as any use of the study device without obtaining informed consent must be reported to AMO within 5 working days. Protocol deviations will be monitored by AMO, and if the non-compliance is persistent or egregious, AMO may take action, including but not limited to termination of the investigator's participation in the study. The investigator is also responsible for informing the reviewing IRB of instances of protocol non-compliance in accordance with the IRB requirements.

## **12. ADVERSE EVENTS AND PRODUCT COMPLAINTS**

### **12.1 ADVERSE EVENT DEFINITIONS**

#### **Adverse Event (AE)**

An adverse event is defined (following ISO 14155) as any untoward medical occurrence, unintended disease or injury, or untoward clinical signs (including abnormal laboratory findings) in subjects, users or other persons, whether or not related to the study device.

#### **Serious Adverse Event (SAE)**

An adverse event is considered serious (following ISO 14155) if it is an untoward occurrence which may or may not be related to use of the study device that

- is sight- or life-threatening,
- results in death,
- requires inpatient hospitalization or prolongation of hospitalization (a planned hospitalization for a pre-existing condition is not considered a serious adverse event),
- results in permanent impairment of a body structure or body function,
- necessitates medical or surgical intervention to prevent permanent impairment to a body structure or function, or
- results in fetal distress, fetal death or a congenital abnormality or birth defect

#### **Device-Related Adverse Event**

A device-related adverse event is defined as any adverse event that is believed to be definitely, probably or possibly related to the study device (following the guidelines in Section 12.4, Causal Relationship). A device-related event is considered an adverse

device effect (ADE; following ISO 14155) resulting from any untoward or unintended response to the study device.

### **Study-Specific Serious Anticipated Adverse Events**

The following is a list including, but not limited to, ocular adverse events that are anticipated and must be reported to AMO for this study. Any events that are unlikely but anticipated (i.e., endophthalmitis) will be reported to the FDA and other appropriate regulatory agencies.

- Endophthalmitis/Intraocular infection
- Hypopyon
- Hyphema
- IOL dislocation
- Cystoid macular edema
- Pupillary block
- Retinal detachment/tear
- Persistent corneal edema
- Persistent iritis
- Persistent raised IOP requiring treatment
- Axis misalignment requiring secondary surgical intervention (e.g., repositioning)
- Tilt and decentration requiring secondary surgical intervention (e.g., repositioning)
- Residual refractive error resulting in a secondary surgical intervention
- Residual lens remnants resulting in a secondary surgical intervention
- Visual symptoms requiring secondary surgical intervention

**NOTE 1:** Wound burps during the first week postoperatively, suture removal, planned blepharoplasty and Nd:YAG capsulotomy (for PCO) are not considered adverse events for this study.

**NOTE 2:** Raised IOP requiring treatment, cornea edema, and iritis will only be considered serious if persistent at the final study visit (120-180 days postoperative) or sight-threatening at the time of occurrence. Treatment merely to hasten the resolution of such conditions (and not intended to prevent permanent damage to the eye) will not be reported as serious adverse events.

### **Unanticipated Adverse Device Effect (UADE)/Unanticipated Serious Adverse Device Effect (USADE)**

Any UADE (USA 21CFR 812.3(s)) or USADE (ISO 14155) is defined as any serious adverse effect on health or safety or any life-threatening problem or death caused by, or associated with, a device, if that effect, problem, or death was not previously identified in nature, severity, or degree of incidence in the investigational plan (i.e., this protocol),

application (including a supplementary plan or application), or risk assessment, or any other unanticipated serious problem associated with a device that relates to the rights, safety, or welfare of subjects.

## **12.2 PRODUCT COMPLAINT/DEVICE DEFICIENCY DEFINITION**

A product complaint/device deficiency is defined (21 CFR 820.3(b) and ISO 14155) as any alleged deficiency related to the identity, quality, durability, reliability, safety, effectiveness, or performance of a device. Product complaints can pertain to any marketed AMO device being used in the study. The investigator is to assess whether the deficiency could have led to a serious adverse event without suitable action or intervention or under less fortunate circumstances.

## **12.3 ADVERSE EVENT AND COMPLAINT REPORTING REQUIREMENTS**

All adverse events and any complaint encountered using any AMO product, regardless of severity and whether or not attributed to the study device(s), are to be reported to AMO and recorded on the case report form corresponding to the visit during which awareness of the event occurred. All serious adverse events, whether anticipated or unanticipated, and all adverse device effects shall be reported using a serious or device related adverse event case report form and forwarded to AMO. Adverse events are also to be reported to the reviewing IRB as per the IRB's reporting requirements. If required, adverse events will be reported to the appropriate regulatory agencies (e.g., FDA) according to all applicable laws and regulations. Specific instructions on notification procedures to AMO are included in **Appendix D**, Adverse Event Reporting.

Reporting of adverse events shall follow the USA Code of Federal Regulations (21CFR812) for sites in the USA. General guidelines are provided below:

### **Adverse Event Reporting**

An adverse event that is not serious or device-related is to be reported to AMO in a timely manner. Notification of non-serious and non-device related adverse events will occur by recording events on the CRF when noted. Such adverse events are also to be reported to the reviewing IRB per their reporting requirements.

### **Complaints/Device Deficiency Reporting**

A general product complaint or device deficiency is to be reported to AMO in a timely manner. Notification of complaints/device deficiencies will occur by either recording complaints on the CRF when the complaint occurred (e.g. operative form) or by a phone call to the Sponsor. Any device deficiency that could have led to a serious adverse event without suitable action or intervention, or under less fortunate circumstances, must be reported to the sponsor immediately (no later than 48 hours after detection). Device

deficiencies that could have led to a serious adverse event should also be reported to the investigator's IRB per their reporting requirements.

### **Serious and/or Device-Related Adverse Event Reporting**

In the event of a serious adverse event (SAE), which may or may not be related to use of the study device, or a device-related adverse event, AMO must be notified immediately (no later than 48 hours after detection). Any SAE and/or device-related AE is to be reported by phone and by submitting a completed Serious and/or Device-Related Adverse Event CRF. Any SAE or device-related AE should also be reported to the investigator's IRB per their reporting requirements.

### **Unanticipated Adverse Device Effect (UADE)/Unanticipated Serious Adverse Device Effect (USADE) Reporting**

If during the study, a serious adverse event occurs that may reasonably be regarded as study-device-related and was not previously expected in nature, severity, or degree of incidence, the investigator is to report the UADE/USADE to AMO within 48 hours, and to the investigator's IRB as soon as possible (and no later than 10 working days after learning of the event for sites in the USA as required by 21CFR812).

#### **12.4 CAUSAL RELATIONSHIP**

The investigator should always be alert to adverse events that may be related to the study device or use of the study device (in the implantation procedure). An attempt should be made in every case to determine if the event may be device-related.

The following definitions are to be used as guidelines in determining the relationship between the event and the study devices: .

Definitely related:	There is a definite causal relationship between the adverse event and the device or implantation procedure.
Probably related:	There is a reasonable possibility of a causal relationship between the adverse event and the device or implantation procedure.
Possibly related:	The adverse event has not been determined to be related to the device or implantation procedure, but no other cause has been definitively identified and the device or implantation procedure cannot be ruled out as a possible cause.
Unlikely to be related:	The possibility of a potential causal relationship between adverse event and the device or implantation procedure could exist, but the adverse event is most likely explained by causes other than the device or implantation procedure.
Not related:	There is no possibility of a causal relationship between the adverse event and the device or implantation procedure.

If an adverse event is believed to be definitely, probably or possibly related to the study device, the event will be considered device-related.

